### 7.1.7    **Electrocardiography**

A standard 12-lead ECG will be performed during screening. Patients must rest for at least 5 minutes prior to the ECG recording. The investigator will interpret the ECG using one of the following categories: normal, abnormal but not clinically significant, or abnormal and clinically significant. The date and time the ECG was performed and the following parameters will be recorded: Heart rate, PR interval, QT interval, QRS interval, and QT corrected using Fridericia's formula (preferred) or alternatively by Bazett's formula (if Bazett's is the established site method).

### 7.1.8    **Pregnancy Test**

Serum pregnancy test for women of childbearing potential required during Screening. Subsequent pregnancy test – either serum or urine – to be done  $\leq$  3 days prior to first dose of protocol-indicated treatment (e.g. if prior screening test was done  $>$  3 days before initiating C1D1 treatment, it will need to be repeated), at EOT, and additionally if clinically indicated per study physician.

A woman of childbearing potential (WOCBP) is defined as any female who has experienced menarche who has not undergone surgical sterilization (e.g. bilateral tubal ligation, total hysterectomy, or bilateral oophorectomy) at least 4 weeks prior to first dose of protocol-indicated treatment, or who is not postmenopausal. Menopause is defined clinically as 12 months of amenorrhea in a woman over 45 in the absence of other biological or physiological causes.

### 7.1.9    **Bone marrow aspiration and biopsy**

Patients must have at least 2-3 mL of bone marrow aspirate material obtained within 14 days of beginning treatment on this study.

On a day of a fresh biopsy procedure, matching peripheral Pharmacodynamic (PD) blood samples are to be drawn PRIOR to the fresh biopsy procedure (with the PD blood to be drawn ideally coincident with any Hematology and Blood Chemistry specimens – if such safety labs are also scheduled for collection on the day in question).

### 7.1.10 Pharmacodynamic (PD) Blood Samples

Pharmacodynamic blood samples for research are to be obtained during Screening (any time prior to first dose of study treatment if archival tissue is used to satisfy the requirement of baseline tumor tissue; or if a fresh baseline biopsy is done, then PD blood should be collected on the same-day as the biopsy – PRIOR to the biopsy procedure).

Blood sampling for PD correlative studies will be done as summarized in the Lab Manual.

## 7.2 Screening (Day -14 to Day -1)

### 7.2.1 Screening Procedures

Screening will include the screening procedures described below and will be performed within 14 days prior to the start of therapy (e.g., day -14 to day -1). Screening activities are summarized in [Table 1](#).

The Investigator should not repeat procedures that are performed as part of standard of care (SOC), if they are within the screening window and are done prior to signing the ICF. Data from SOC procedures will be part of the patient's medical history and may be used for study purposes.

Prior to performing any study-based procedures, patient informed consent must be obtained. Screening may be divided into two (or more) clinic visits at the discretion of the Investigator. The procedures to be performed during screening are listed below:

- Informed consent and baseline characteristics
- Physical Exam
- ECOG performance status
- Height and weight
- Vital signs: Blood pressure (BP), heart rate (HR) and temperature.
- Concomitant medication and adverse event review.
- CBC with differential
- Blood chemistry including magnesium, phosphorus, LDH, and uric acid
- Coagulation testing (PT/INR, PTT)
- Electrocardiogram (ECG)
- Serum or urine pregnancy test in women of childbearing potential
- Bone marrow aspiration/biopsy with additional aspirate sent for correlative science
- Next generation sequencing (locally done/myeloid focused)
- PD studies (blood)
- Anti-TLS hydration / prophylaxis Allopurinol must be initiated at least 2-3 days prior to the start of therapy.

## 7.2.2 Screen Failures

A patient found not eligible for the trial after giving informed consent is considered a screen-failure. The enrollment form must be completed and sent to the sponsor-investigator or designee to confirm the outcome of the screening process.

Re-screening and re-enrollment of a subject who has discontinued the study as a pre-treatment failure (e.g. subject has not received protocol-indicated treatment) is permitted.

A consented patient previously reported to the coordinating center as pre-treatment failure must be re-consented prior to undergoing re-screening.

## 7.3 Cycle 1 (Pre-remission Therapy)

### 7.3.1 Cycle 1, Day 1

On Cycle 1, Day 1, the following procedures must be completed, unless previously completed  $\leq$  3 days prior to a patient's first dose of protocol-indicated treatment:

- Physical Exam
- ECOG performance status
- CBC with differential
- Blood chemistry including magnesium, phosphorus, LDH, and uric acid
- Serum or urine pregnancy test in women of childbearing potential
- Weight.
- Vital Signs: Blood pressure (BP), heart rate (HR) and temperature.
- Concomitant medication and Adverse Event review.
- Surveillance for and expedited reporting of Dose Limiting Toxicity (DLT) – see [Section 5.2.4](#) for DLT definition.
- Anti-TLS hydration / prophylaxis
- Dose venetoclax/DEC-C as outlined in [Table 5](#) and [Table 6](#).

### 7.3.2 Cycle 1, Day 2, 3, & 5

- CBC with differential
- Blood chemistry including magnesium, phosphorus, LDH, and uric acid
- Vital Signs: Blood pressure (BP), heart rate (HR) and temperature.
- Concomitant medication and Adverse Event review.
- Surveillance for and expedited reporting of Dose Limiting Toxicity (DLT) – see [Section 5.2.4](#) for DLT definition.
- Anti-TLS hydration / prophylaxis
- Dose venetoclax/DEC-C as outlined in [Table 5](#) and [Table 6](#).

### 7.3.3 Cycle 1, Day 8

- CBC with differential

- Blood chemistry including magnesium, phosphorus, LDH, and uric acid
- Vital Signs: Blood pressure (BP), heart rate (HR) and temperature.
- Concomitant medication and Adverse Event review.
- Surveillance for and expedited reporting of Dose Limiting Toxicity (DLT) – see [Section 5.2.4](#) for DLT definition.
- Anti-TLS hydration / prophylaxis
- Dose venetoclax as outlined in [Table 5](#) and [Table 6](#).

#### 7.3.4 Cycle 1, Day 15

- CBC with differential
- Blood chemistry
- Vital Signs: Blood pressure (BP), heart rate (HR) and temperature.
- Concomitant medication and Adverse Event review.
- Surveillance for and expedited reporting of Dose Limiting Toxicity (DLT) – see [Section 5.2.4](#) for DLT definition.
- Anti-TLS hydration / prophylaxis
- Dose venetoclax as outlined in [Table 5](#) and [Table 6](#).

#### 7.3.5 Cycle 1, Day 22

- CBC with differential
- Blood chemistry
- Vital Signs: Blood pressure (BP), heart rate (HR) and temperature.
- Concomitant medication and Adverse Event review.
- Surveillance for and expedited reporting of Dose Limiting Toxicity (DLT) – see [Section 5.2.4](#) for DLT definition.
- Anti-TLS hydration / prophylaxis
- Dose venetoclax as outlined in [Table 5](#) and [Table 6](#).
- Bone marrow aspiration/biopsy with additional aspirate sent for correlative science
- Next generation sequencing (Central/VUMC)
- PD studies (blood)

### 7.4 Cycle 2 (Pre-remission Therapy; only if C1D22 marrow is involved)

#### 7.4.1 Cycle 2, Day 1

- Physical Exam
- ECOG performance status
- Weight.
- Vital Signs: Blood pressure (BP), heart rate (HR) and temperature.
- Concomitant medication and Adverse Event review.
- CBC with differential
- Blood chemistry

- Surveillance for and expedited reporting of Dose Limiting Toxicity (DLT) – see [Section 5.2.4](#) for DLT definition.
- Dose venetoclax/DEC-C as outlined in [Table 5](#) and [Table 6](#).

#### 7.4.2 Cycle 2, Day 8

- Vital Signs: Blood pressure (BP), heart rate (HR) and temperature.
- Concomitant medication and Adverse Event review.
- CBC with differential
- Blood chemistry
- Dose venetoclax as outlined in [Table 5](#) and [Table 6](#).

#### 7.4.3 Cycle 2, Day 15

- Physical Exam
- Vital Signs: Blood pressure (BP), heart rate (HR) and temperature.
- Concomitant medication and Adverse Event review.
- CBC with differential
- Blood chemistry
- Dose venetoclax as outlined in [Table 5](#) and [Table 6](#).

#### 7.4.4 Cycle 2, Day 22

- Physical Exam
- Vital Signs: Blood pressure (BP), heart rate (HR) and temperature.
- Concomitant medication and Adverse Event review.
- CBC with differential
- Blood chemistry
- Dose venetoclax as outlined in [Table 5](#) and [Table 6](#).
- Bone marrow aspiration/biopsy with additional aspirate sent for correlative science
- Next generation sequencing (Central/VUMC)
- PD studies (blood)

### 7.5 Post-remission Cycle 1 (if remission confirmed/counts recovered)

#### 7.5.1 Post-remission Cycle 1, Day 1

- Physical Exam
- ECOG performance status
- Weight.
- Vital Signs: Blood pressure (BP), heart rate (HR) and temperature.
- Concomitant medication and Adverse Event review.
- CBC with differential
- Blood chemistry
- Surveillance for and expedited reporting of Dose Limiting Toxicity (DLT) – see [Section 5.2.4](#) for DLT definition (**only in patients who received one pre-remission cycle**)

- Dose venetoclax/DEC-C as outlined in [Table 5](#) and [Table 6](#).

### 7.5.2 Post-remission Cycle 1, Day 5

- Vital Signs: Blood pressure (BP), heart rate (HR) and temperature.
- Concomitant medication and Adverse Event review.
- CBC with differential
- Blood chemistry
- Dose venetoclax/DEC-C as outlined in [Table 5](#) and [Table 6](#).

### 7.5.3 Post-remission Cycle 1, Day 15

- Vital Signs: Blood pressure (BP), heart rate (HR) and temperature.
- Concomitant medication and Adverse Event review.
- CBC with differential
- Blood chemistry
- Dose venetoclax as outlined in [Table 5](#) and [Table 6](#).

## 7.6 Post-remission Cycle 2 (if remission confirmed/counts recovered)

### 7.6.1 Post-remission Cycle 2, Day 1

- Physical Exam
- ECOG performance status
- Weight.
- Vital Signs: Blood pressure (BP), heart rate (HR) and temperature.
- Concomitant medication and Adverse Event review.
- CBC with differential
- Blood chemistry
- Surveillance for and expedited reporting of Dose Limiting Toxicity (DLT) – see [Section 5.2.4](#) or DLT definition (**only in patients who received one pre-remission cycle**)
- Dose venetoclax/DEC-C as outlined in [Table 5](#) and [Table 6](#).

### 7.6.2 Post-remission Cycle 2, Day 5

- Vital Signs: Blood pressure (BP), heart rate (HR) and temperature.
- Concomitant medication and Adverse Event review.
- CBC with differential
- Blood chemistry
- Dose venetoclax/DEC-C as outlined in [Table 5](#) and [Table 6](#).

### 7.6.3 Post-remission Cycle 2, Day 15

- Vital Signs: Blood pressure (BP), heart rate (HR) and temperature.
- Concomitant medication and Adverse Event review.
- CBC with differential

- Blood chemistry
- Dose venetoclax as outlined in [Table 5](#) and [Table 6](#).

## 7.7 Post-remission Cycle 3 (only if remission confirmed/counts recovered)

### 7.7.1 Post-remission Cycle 3, Day 1

- Physical Exam
- ECOG performance status
- Weight.
- Vital Signs: Blood pressure (BP), heart rate (HR) and temperature.
- Concomitant medication and Adverse Event review.
- CBC with differential
- Blood chemistry
- Dose venetoclax/DEC-C as outlined in [Table 5](#) and [Table 6](#).
- Bone marrow aspiration/biopsy with additional aspirate sent for correlative science
- Next generation sequencing (Central/VUMC)

## 7.8 Post-remission Cycle 4+ (if remission confirmed/counts recovered)

### 7.8.1 Post-remission Cycle 4+, Day 1

- Physical Exam
- ECOG performance status
- Weight.
- Vital Signs: Blood pressure (BP), heart rate (HR) and temperature.
- Concomitant medication and Adverse Event review.
- CBC with differential
- Blood chemistry
- Dose venetoclax/DEC-C as outlined in [Table 5](#) and [Table 6](#).

### 7.8.2 End of Treatment ( $\leq$ 10 days after last dose of study treatment)

Reasonable effort should be made to complete End-of-Treatment (EOT) / Withdrawal procedures on the day it is decided that a patient will no longer receive protocol-indicated treatment.

The following EOT procedures must be completed subsequent to and not later than 10 days after the patient's last dose of protocol-indicated treatment with venetoclax/DEC-C (whichever treatment occurs last) and prior to any subsequent anti-cancer therapy:

- Physical Exam
- ECOG performance status
- Weight
- Vital signs: Blood pressure (BP), heart rate (HR) and temperature.
- Concomitant medication and adverse event review.

- CBC with differential
- Blood chemistry including magnesium, phosphorus, LDH, and uric acid
- Coagulation testing (PT/INR, PTT)
- Electrocardiogram (ECG)
- Serum or urine pregnancy test in women of childbearing potential
- Bone marrow aspiration/biopsy with additional aspirate sent for correlative science
- Next generation sequencing (Central/VUMC)
- PD studies (blood)

## 7.9 28 Day Follow-up Visit Assessments

Documented attempt(s) must be made for patient return to the study clinic. It will not be considered a protocol deviation if the patient is physically unable to return for the follow-up visit; such circumstance should be recorded in the study documents, and as much of the follow-up information as possible should be obtained via feasible patient contact and from local and outside facilities.

A Follow-up clinic visit is to be completed 28 days (+7 days) after patient's final protocol-indicated treatment venetoclax or DEC-C (whichever occurs last), in order to undergo the following assessments:

- Physical Exam
- ECOG performance status
- Weight
- Vital signs: Blood pressure (BP), heart rate (HR) and temperature.
- Concomitant medication and adverse event review.
- CBC with differential
- Blood chemistry

For patients who discontinue study treatment for reason other than progressive disease confirmed by bone marrow aspiration and biopsy (e.g. suspicious peripheral blood counts), please note the study may continue to request results of laboratory data conducted outside of the study but related to peripheral blood counts or bone marrow examination, until progressive disease following venetoclax/DEC-C is ultimately confirmed by marrow procedure.

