11. During the first three days of therapy, tumor lysis syndrome (TLS) precautions will include scheduled outpatient visits with TLS laboratory studies. Therapy with a uric acid reducing agent (e.g., allopurinol initiated at least 2-3 days prior to the start of therapy) is required. Laboratory monitoring for TLS (per institution standard of care) will occur prior to the first dose on cycle 1 day 1 and continue for the first three days of cycle 1. Unless contraindicated, allopurinol must be continued through the end of cycle 1. Intravenous fluids should be administered daily during the ramp-up period. Patients with clinical evidence of TLS should be hospitalized.
12. The study will provide decitabine/cedazuridine (DEC-C) to the sites. Treatment with DEC-C will begin on Cycle 1 Day 1 after receiving anti-TLS hydration/prophylaxis. It is intended that patients will receive DEC-C until progression of disease, unacceptable toxicity, revocation of consent, or for up to 12 months of post-remission therapy. DEC-C is to be taken without food at the same time each day. See [Section 5.2.1.2](#).
13. Sites will obtain commercial (standard of care) venetoclax. Venetoclax will begin on Cycle 1 Day 1 after receiving anti-TLS hydration/prophylaxis. Venetoclax dosing is ramped to 400mg/day. It is intended that patients will receive venetoclax until progression of disease, unacceptable toxicity, revocation of consent, or for up to 12 months of maintenance. Venetoclax is taken with food at the same time each day. See [Section 5.2.1.1](#).
14. On Cycle 1, Day 1 only: Physical exam; ECOG performance status; and weight will be obtained unless performed within the prior 7 days. Confirmation of a negative pregnancy test is required in all women of childbearing potential prior to beginning protocol-directed therapies.
15. All patients will undergo bone marrow aspiration and biopsy on cycle 1 day 22 to assess treatment response and for correlative studies. Patients with at least a partial response (PR) to treatment who receive a second cycle of full-intensity therapy will have repeat biopsy at cycle 2 day 22. Aspirate and matching PD blood samples will be sent for correlative studies.

16. Beginning in the post-remission phase: To accommodate scheduling, Day 1 and 15 visits/procedures may occur with flexibility of  $\pm$  3 days.

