17. Reasonable effort should be made to complete End-of-Treatment (EOT) procedures on the day it is decided a patient will no longer receive protocol-indicated treatment. These procedures must be completed subsequent to and not later than 10 days after investigator decision to permanently discontinue protocol-indicated treatment with DEC-C or venetoclax (whichever treatment occurs last) and prior to any subsequent anti-cancer therapy.
18. At End-of-Treatment: If patient discontinues study treatment for reason other than progressive disease confirmed by biopsy procedure (e.g. due to adverse event), then every effort should be made to obtain fresh biopsy samples to evaluate response and to obtain biospecimens including matching PD blood samples for exploratory research. If progressive disease is suspected between scheduled study biopsies (e.g. due to peripheral blood counts), then fresh biopsy and PD blood samples must be collected in a subsequent procedure to evaluate for progressive disease and to obtain bio specimens for research purposes; if progressive disease is confirmed in that procedure and the patient will terminate the study as a result, then these procedures may be used as the end of treatment procedures.
19. Follow-up clinic visit to be completed within 28 to 35 days after patient's final protocol-indicated treatment with DEC-C or venetoclax (whichever occurs last). Documented attempt(s) must be made for patient return to the study clinic. It will not be considered a protocol deviation if the patient is physically unable to return for the follow-up visit; such circumstance should be recorded in the study documents, and as much of the follow-up information as possible should be obtained from local and outside facilities. Note: The study may continue to request results of laboratory data conducted outside of the study but related to peripheral blood counts or bone marrow biopsy, until progressive disease is ultimately confirmed.
20. Each patient will be followed for survival every 3 months ( $\pm$  14 days) after patient's final protocol treatment with DEC-C or venetoclax (whichever occurs last) until death, end of the study, until patient withdraws consent, or for a maximum of 2 years after the patient's final protocol-indicated treatment – whichever comes first. Survival contact can be made via clinic visit, chart review, obituary or similar observation (e.g. Social Security death index), or by telephone.

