### **2.2 Secondary Objectives:**

1. To assess the rate of partial response (PR) and morphologic leukemia free state (MLFS) following treatment with DEC-C/venetoclax
2. To assess the relapse free survival of patients treated with DEC-C/venetoclax
3. To assess overall survival of patients treated with DEC-C/venetoclax
4. To assess the safety and tolerability of DEC-C/venetoclax in the post-HCT setting
5. To assess the rates of measurable residual disease negativity in patients achieving a CR.

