### 5.2.13 Off-Treatment Criteria

Participants will be removed from study when any of the following criteria apply:

- Disease progression
- Unacceptable toxicity
- Lost to follow-up
- Withdrawal of consent

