## 7.10 Survival Follow-up

Each patient will be followed for survival every 3 months ( $\pm$  14 days) after patient's final protocol treatment with DEC-C or venetoclax (whichever occurs last) until death, end of the study, until patient withdraws consent, or for a maximum of 2 years after the patient's final protocol-indicated treatment – whichever comes first. Survival contact can be made via clinic visit, chart review, obituary or similar observation (e.g. Social Security death index), or by telephone.

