### 9.3.1 General Analysis Considerations

Continuous variables (e.g., age) will be summarized using the minimum, 25th, 50th (median), 75th, and maximum values along with the mean and standard deviation, as appropriate. Generally, rank based nonparametric tests will be used to compare continuous variables among patient subgroups. Categorical variables (e.g., objective response) will be summarized in frequency tables and compared among patient subgroups using the chi-square test. Linear regression and logistic (or ordinal logistic) regression will be used to construct multivariable models for continuous, binary, and ordinal variables, as appropriate. In addition to ORR, the distributions of progression-free and overall survival will be estimated using the Kaplan-Meier method. We will consider statistical comparisons statistically, but not necessarily clinically, significant for  $p<0.05$ .

Dose limiting toxicity (see [Section 5.2.4](#)) will be monitored in this phase II clinical trial using a Bayesian approach. A maximum of 34 patients will be enrolled and toxicity monitoring will begin when the 6th patient is evaluable for toxicity. It is expected that the toxicity rate is maintained at approximately 20% (maximum probability of DLT of 0.2, prior distribution (1,1), cohort size 1, and posterior probability  $> 80\%$ ). Pursuant to this rule, patients will be monitored according to the stopping boundaries outlined in [Table 10](#). For example, the protocol will pause for review due to excessive toxicity if 2 or more DLTs are experienced by the first 6 patients treated. 9 DLTs will be allowed among 34 patients treated.

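### After treatment stops without confirmed progression, relapse follow-up beyond the 28- to 35-day visit is optional and unscheduled, although relapse-free survival is a secondary objective

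*Combined protocol and SAP*

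**What the plan says.** **Endpoints that need relapse dates.** Section 2.2 lists as an objective: "To assess the relapse free survival of patients treated with DEC-C/venetoclax". Section 9.3.1 states that "the distributions of progression-free and overall survival will be estimated using the Kaplan-Meier method". Section 9 gives no RFS definition and no censoring rule.

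**Ways off treatment without progression.** Note 12 to the schedule of activities limits DEC-C to progression, unacceptable toxicity, revoked consent, "or for up to 12 months of post-remission therapy". Note 13 sets a matching 12-month limit for venetoclax. Section 5.2.13 adds unacceptable toxicity, loss to follow-up and withdrawal of consent, under the lead-in "Participants will be removed from study when any of the following criteria apply".

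**Last scheduled disease tests.** The last scheduled marrow is at end of treatment (Section 7.8.2; Tables 2 and 3). The last scheduled blood count is at the follow-up visit 28 days (+7) after the last dose (Section 7.9).

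**After that visit.** For patients who stopped for a reason other than marrow-confirmed progression, Section 7.9 says "the study may continue to request results of laboratory data conducted outside of the study" until progression is confirmed. Note 19 matches it: "The study may continue to request results of laboratory data conducted outside of the study but related to peripheral blood counts" or marrow. Section 7.10 and Note 20 then require survival follow-up every 3 months for at most 2 years after the last treatment. On method: "Survival contact can be made via clinic visit, chart review, obituary or similar observation (e.g. Social Security death index), or by telephone".

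**The concern.** A responder who finishes 12 months of post-remission therapy, or who stops for toxicity while in remission, is still at risk of relapse. For that patient the plan obliges sites to find out about death but not about relapse. An obituary or death index satisfies Section 7.10 and carries no relapse date.

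The indirect routes are not required either. Adverse events and concomitant medications need to be collected only to about 28 days after treatment (Note 3; Sections 7.1.4 and 7.1.5), so the start of a new anti-leukemic drug, a usual marker of relapse, need not be recorded later. The mandatory biopsy on suspicion in Note 18 is worded for the time between scheduled study biopsies, and end of treatment is the last of these.

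A relapse that nobody requests then enters the analysis late, at death, or not at all. RFS and PFS would look better than they are, and the amount could differ between sites in a multi-center trial.

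**Working it through.** The plan states no figure on this point to reproduce. The check is a reading of the schedule plus simple arithmetic.

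**1. What is required after the last dose**

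| Period | Disease status | Survival |
|---|---|---|
| End of treatment | Marrow, blood count (7.8.2) | Covered by the visit |
| 28 to 35 days | Blood count, no marrow (7.9) | Covered by the visit |
| After that, to 2 years | Optional request for outside results (7.9, Note 19) | Every 3 months (7.10, Note 20) |

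**2. Longest possible gap**
- Survival contacts: 24 / 3 = 8 at most.
- Months without a scheduled disease test: 24 − 28/30.44 = 23.1, or 24 − 35/30.44 = 22.9. The ceiling is about 23 months.

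**3. What the calendar does to that ceiling.** Section 3.2 estimates enrollment from January 2022 to January 2024 and data lock in January 2025. A patient who completes treatment has at least one pre-remission cycle (about 1 month) plus 12 months, so about 13 months on treatment.
- Enrolled January 2022: 36 − 13 = 23 months from last dose to lock; less 1 month to the follow-up visit, about 22.
- Enrolled January 2023: 24 − 13 = 11; less 1, about 10.
- Enrolled January 2024: 12 − 13 is below zero, so none.

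The full 23 months needs a last dose by about January 2023, which in practice means an early stop such as one for toxicity.

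**4. Effect of one missed relapse.** The documents do not define the RFS population. Assume it is the responders, with nobody censored earlier. One responder who has relapsed but is alive and unrecorded raises the estimate at that time by 1/n:
- Design rate 35%: 34 × 0.35 = 11.9, about 12 responders; 1/12 = 8.3 points.
- Section 9.3 boundary of more than 9 of 34, so at least 10: 1/10 = 10.0 points.
- The center's own series, ORR 42.1%: 34 × 0.421 = 14.3, about 14; 1/14 = 7.1 points.
- PFS in all 34 patients: 1/34 = 2.9 points.

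**5. How many patients could be exposed.** The documents do not give the share of responders who stop without progression. Assumed shares of 10%, 25% and 50% of 12 give 1.2, 3.0 and 6.0 patients. These are patients in the gap, not missed relapses. No relapse or non-reporting probability is applied, because none is available.

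**6. Hypothetical illustration (all times assumed).** Take 12 responders with 6 relapses by month 12, so true 12-month RFS = 6/12 = 0.500. Suppose 2 of the 6 stopped early, relapsed unrecorded, and died at months 14 and 16.
- Events dated at death: 8/12 = 0.667.
- Those 2 censored at their last visits (months 6.1 and 7), with three recorded relapses before and one after: 9/12 × 6/7 = 0.643. Depending on the order of events, this ranges from 6/10 = 0.600 to 8/12 = 0.667.

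This shows direction only. Patients who complete 12 months of post-remission therapy are still under scheduled visits at month 12 and could not cause this particular error.

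**The case against.** The strongest reply is that the plan does provide a source. Section 7.9 and Note 19 cover every patient who stops without marrow-confirmed progression and show an intent to follow until progression is confirmed. Clinic visit and chart review are the first two contact methods in Section 7.10, and either could reveal a relapse. A reader might infer that RFS has no source of relapse dates at all after the 28-day visit. The documents do not support that: a source exists, but it is optional and has no timetable.

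Coverage before the gap is also good: a blood count every cycle, a marrow at post-remission Cycle 3 Day 1, a biopsy on suspected progression, and a marrow at end of treatment. The gap opens only after disease status has been sought at end of treatment. The 23 months is a ceiling that most patients will not reach, and the 12-month illustration is constructed. RFS is a secondary, single-arm estimate that drives no decision rule.

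All of this stands, and it limits the size of the problem. It does not remove it: nothing obliges a site to ask about relapse at a contact it must make anyway, and nothing obliges it to record what it learns.

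A reader might also take the lead-in to Section 5.2.13 to mean that survival follow-up ends with treatment. The section is titled as off-treatment criteria, and Section 7.10 settles that survival follow-up continues.

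**Conclusion.** The concern holds in a limited form. Between the 28- to 35-day visit and the end of survival follow-up, RFS and PFS have scheduled death dates but no required relapse dates for patients who stopped without confirmed progression. Unrecorded relapses in living patients would bias both estimates upward.

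The size cannot be derived from the documents. It is zero if every site reports every relapse. Per missed relapse it is about 7 to 10 points of RFS, if RFS is estimated in 10 to 14 responders without earlier censoring, and 2.9 points of PFS in 34 patients. The window is at most about 23 months and shorter for most patients. A firm claim that RFS will be overstated by a given amount would go beyond the documents.

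The primary composite CR test, the Simon boundaries, the DLT rules and overall survival are not touched. The change is worth making because it improves the data at almost no cost, and a relapse date not collected at the time may be hard to recover later.

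**What to change.** - **Section 7.10 and Note 20.** For each patient without documented relapse or progression at end of treatment, record at every 3-month contact the relapse status, its date and source, and the start of any new anti-leukemic therapy. Use chart review or the treating clinic where possible, since an obituary or death index cannot supply these.
- **Section 7.9 and Note 19.** Replace *may continue to request* with *will request*, tied to the same contacts.
- **Section 9.3.1.** Count relapse or death as the RFS event. Censor living patients without relapse at the last date on which relapse-free status was documented, whether by test result, clinic record or contact. Report how many patients had no relapse status after the 28-day visit. Censoring only at the last blood count or marrow would discard the status gathered at the new contacts. It would also let deaths be observed for longer than relapse-free survival, which could bias RFS downward.
- **Section 5.2.13 (optional).** Write that participants are removed from study *treatment*, and refer to Sections 7.9 and 7.10.

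The cost is a few case report form items at no more than 8 contacts per patient, all already planned, plus the wording changes. No extra visit or marrow is needed.
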